## 2.4 Correlative Studies Background

### 2.4.1 Molecular Correlatives

Our objectives are to use next generation sequencing technologies to identify genetic predictors of response to immune checkpoint inhibitor blockade using clinical samples collected as part of clinical care. Our group has extensive experience in genomic characterization of a number of brain tumors including craniopharyngioma, brain metastases and their matched peripheral primaries and meningioma. We will use whole exome or targeted exome sequencing panels that cover genes implicated in meningioma development and progression to identify markers of response. We will characterize mutations, gene rearrangements and copy number alterations from this data. RNA-sequencing will also be used to identify signatures of response. We will also characterize and quantify the levels of PD-1 and PD-L1 mRNA expression in the tumor samples using an in situ hybridization technology (RNAscope) as well as to characterize the immune infiltrate using immunohistochemistry markers and image quantification. Our goal is to use these techniques to identify genetic, mRNA and proteomic predictors of response to checkpoint inhibitors.

### 2.4.2 Imaging Correlatives

MRI is a very useful tool to non-invasively probe tumor response to treatment and is already part of the routine management of patients with meningioma. Imaging correlatives will be performed as outlined in Section 9.3.5.

## 3.0 PARTICIPANT SELECTION

### 3.1 Eligibility Criteria

#### 3.1.1 Documentation Of Disease

**Histologic Documentation:** Histologically proven recurrent or residual intracranial or metastatic meningioma or meningioma with extracranial spread

**Progressive OR residual disease**, as defined by the following:

**Progressive disease**, as defined as an increase in size of a measurable meningioma lesion on imaging by greater than 25% (bidirectional area). The change must occur between scans separated by no more than 24 months.

**Residual measurable disease:** For Grade II or III meningioma, residual measurable disease immediately after surgery without requirement for progression. Residual measurable disease will be defined by measurable lesions with clearly defined margins by MRI scans, with a minimum diameter of 10mm in one dimension.

**Post radiation patients:** Patients with measurable and progressive meningioma who have received radiation are potentially eligible, but need to show evidence of progressive disease in the radiated field after completion of radiation.  $\geq 24$  weeks must have elapsed from completion of radiation to registration. Patients that have progressive disease outside of the radiation field do not need to wait 24 weeks from completion of radiation.

**3.1.2 Measurable Disease:** Measurable disease is defined by a main lesion measurable on MRI or CT images (MRI preferred) with clearly defined margins and  $\geq 10$  mm in one dimension. Multifocal disease is allowed as long as one lesion meets criteria for measurable disease and progressive disease. For measurable disease, refer to Section 11.0

**3.1.3 Prior Treatment**

- Prior medical therapy is allowed but not required.
- Meningioma that have resulted from prior radiation therapy are allowed.
- No limit on number of prior therapies.
- No chemotherapy, other investigational agents within 14 days of study treatment.
- No other concurrent investigational agents or other meningioma-directed therapy (chemotherapy, radiation) while on study.
- For patients treated with external beam radiation, interstitial brachytherapy or radiosurgery, an interval  $\geq 24$  weeks must have elapsed from completion of XRT to registration.
- Stable dose of dexamethasone 2mg or less for at least 7 days prior to initiation of treatment.
- Recovered to CTCAE grade 1 or less toxicity from other agents with exception of alopecia and fatigue.
- No craniotomy within 21 days of registration.
- Grade I meningiomas will be allowed as long as they meet criteria for progression as defined by 3.1.1.

**3.1.4 Not pregnant and not nursing:**

A female of childbearing potential is a sexually mature female who: 1) has not undergone a hysterectomy or bilateral oophorectomy; or 2) has not been naturally postmenopausal for at least 12 consecutive months (i.e., has had menses at any time

in the preceding 12 consecutive months). Female subject of childbearing potential should have a negative urine or serum pregnancy within 72 hours prior to receiving the first dose of study medication. If the urine test is positive or cannot be confirmed as negative, a serum pregnancy test will be required. Female subjects of childbearing potential should be willing to use 2 methods of birth control or be surgically sterile, or abstain from heterosexual activity for the course of the study through 120 days after the last dose of study medication.

**3.1.5 Age  $\geq$  18 years**

**3.1.6 ECOG Performance Status  $\leq$  2**

**3.1.7 Patient history:** Patients with history of NF may have other stable CNS tumors (schwannoma, acoustic neuroma or ependymoma) if lesions have been stable for 6 months.

**3.1.8** Metastatic meningiomas (as defined by extracranial meningiomas) and meningioma with extra-cranial spread are allowed.

**3.1.9 Required Initial Laboratory Values**

Participants must have normal organ and marrow function as defined in Table 1, all screening labs should be performed within 14 days of treatment initiation.

Table 1: Required Initial Laboratory Values	
System	Laboratory Value
Hematological	
Absolute neutrophil count (ANC)	$\geq 1,500$ /mcL
Platelets	$\geq 100,000$ / mcL
Hemoglobin	$\geq 9$ g/dL or $\geq 5.6$ mmol/L without transfusion or EPO dependency (within 7 days of assessment)
Renal	
Serum creatinine OR Measured or calculated a creatinine clearance (GFR can also be used in place of creatinine or CrCl)	$\leq 1.5$ X upper limit of normal (ULN) OR $\geq 60$ mL/min for subject with creatinine levels $> 1.5$ X institutional ULN
Hepatic	
Serum total bilirubin	$\leq 1.5$ X ULN OR Direct bilirubin $\leq$ ULN for subjects with total bilirubin levels $> 1.5$ ULN
AST (SGOT) and ALT (SGPT)	$\leq 2.5$ X ULN
Albumin	$\geq 2.5$ g/dL
Coagulation	
International Normalized Ratio (INR) or Prothrombin Time	$\leq 1.5$ X ULN unless subject is receiving anticoagulant therapy

(PT)		as long as PT or PTT is within therapeutic range of intended use of anticoagulants
Activated Thromboplastin Time (aPTT)	Partial	$\leq 1.5 \times \text{ULN}$ unless subject is receiving anticoagulant therapy
		as long as PT or PTT is within therapeutic range of intended use of anticoagulants
a Creatinine clearance should be calculated per institutional standard.		

- 3.1.10 Male subjects should agree to use an adequate method of contraception starting with the first dose of study therapy through 120 days after the last dose of study therapy.
- 3.1.11 Ability to understand and the willingness to sign a written informed consent document.

**3.2 Exclusion Criteria**

- 3.2.1 Participants who have had chemotherapy, targeted small molecule therapy or study therapy within 14 days of protocol treatment, or those who have not recovered (i.e.,  $\leq$  Grade 1 or at baseline) from adverse events due to agents administered more than 2 weeks earlier. Subjects with  $\leq$  Grade 2 neuropathy are an exception to this criterion and may qualify for the study. If subject received major surgery, they must have recovered adequately from the toxicity and/or complications from the intervention prior to starting therapy.
- 3.2.2 Participants with brainstem lesions
- 3.2.3 Participants who are receiving any other investigational agents.
- 3.2.4 Participants who have a diagnosis of an immunodeficiency.
- 3.2.5 Requires treatment with high dose systemic corticosteroids defined as dexamethasone  $>2\text{mg/day}$  or bioequivalent within at least 7 days of initiating therapy.
- 3.2.6 Has received systemic immunosuppressive treatments, aside from systemic corticosteroids as described in Section 5.7, within three months of start of study drug
- 3.2.7 Has a known hypersensitivity to pembrolizumab or any of its excipients
- 3.2.8 Has a known history of active TB (Bacillus Tuberculosis)
- 3.2.9 Uncontrolled intercurrent illness including, but not limited to, ongoing or active infection, symptomatic congestive heart failure, unstable angina pectoris, cardiac arrhythmia, or psychiatric illness/social situations that would limit compliance with study requirements.
- 3.2.10 Has known psychiatric or substance abuse disorders that would interfere with cooperation with the requirements of the trial.
- 3.2.11 Is pregnant or breastfeeding, or expecting to conceive or father children within the projected duration of the trial, starting with the pre-screening or screening visit through 120 days after the last dose of trial treatment.
- 3.2.12 Has a known additional malignancy that is progressing or requires active treatment. Exceptions include basal cell carcinoma of the skin or squamous cell carcinoma of the skin that has undergone potentially curative therapy or in situ cervical cancer or stable NF-related neoplasms (Section 3.1.7).
- 3.2.13 Has active autoimmune disease that has required systemic treatment in the past 2

- years (i.e. with use of disease modifying agents, corticosteroids or immunosuppressive drugs). Replacement therapy (eg., thyroxine, insulin, or physiologic corticosteroid replacement therapy for adrenal or pituitary insufficiency, etc.) is not considered a form of systemic treatment.
- 3.2.14 Has known history of, or any evidence of active, non-infectious pneumonitis.
  - 3.2.15 Has a known active infection requiring systemic therapy.
  - 3.2.16 Has received prior therapy with an anti-PD-1, anti-PD-L1, or anti-PD-L2 agent.
  - 3.2.17 Has a known history of Human Immunodeficiency Virus (HIV) (HIV 1/2 antibodies). HIV-positive participants on combination antiretroviral therapy are ineligible because of the potential for pharmacokinetic interactions with pembrolizumab. In addition, these participants are at increased risk of lethal infections when treated with marrow-suppressive therapy. Appropriate studies will be undertaken in participants receiving combination antiretroviral therapy when indicated.
  - 3.2.18 Has known active Hepatitis B (e.g., HBsAg reactive) or Hepatitis C (e.g., HCV RNA [qualitative] is detected).
  - 3.2.19 Has received a live vaccine within 30 days of planned start of study therapy. Note: Seasonal influenza vaccines for injection are generally inactivated flu vaccines and are allowed; however intranasal influenza vaccines (e.g., Flu-Mist®) are live attenuated vaccines, and are not allowed.
  - 3.2.20 Unable to undergo brain MRI.

### **3.3 Inclusion of Women and Minorities**

Both men and women of all races and ethnic groups are eligible for this trial.

## **4. REGISTRATION PROCEDURES**

### **4.1 General Guidelines for DF/HCC Institutions**

Institutions will register eligible participants in the Clinical Trials Management System (CTMS) OnCore. Registrations must occur prior to the initiation of protocol therapy. Any participant not registered to the protocol before protocol therapy begins will be considered ineligible and registration will be denied.

An investigator will confirm eligibility criteria and a member of the study team will complete the protocol-specific eligibility checklist.

Following registration, participants may begin protocol therapy. Issues that would cause treatment delays should be discussed with the Overall Principal Investigator (PI). If a participant does not receive protocol therapy following registration, the participant's registration on the study must be canceled. Registration cancellations must be made in OnCore as soon as possible.

### **4.2 Registration Process for DF/HCC Institutions**

DF/HCC Standard Operating Procedure for Human Subject Research Titled *Subject Protocol Registration* (SOP #: REGIST-101) must be followed.

## 5. TREATMENT PLAN

### 5.1 Treatment Regimen

Pembrolizumab will be administered every 3 weeks, with 21 consecutive days defined as a treatment cycle. Treatment will be administered on an outpatient basis. Reported adverse events and potential risks are described in Section 7. Appropriate dose modifications are described in Section 6. No investigational or commercial agents or therapies other than those described below may be administered with the intent to treat the participant's malignancy.

The treatment to be used in this trial is outlined below in the table below.

Table 2: Dose of Pembrolizumab

Drug	Dose/Potency	Dose Frequency	Route of Administration	Regimen/Treatment Period	Cycle Length
Pembrolizumab	200 mg	Q3W	IV infusion	Day 1 of each 3 week cycle	3 weeks

### 5.2 Pre-Treatment Criteria

Informed consent will be obtained after the study has been fully explained to the subject and before the conduct of any screening procedures or assessments. If screening assessments occur within 7 days before start of study treatment, then they may serve as the baseline Cycle 1 Day 1 study tests and do not need to be repeated.

Pretreatment criteria will be assessed within 14 days of the first dose of study treatment to establish eligibility and baseline values. This will be considered the baseline clinical evaluation. Subsequent changes from screening physical exam (PE) findings that meet the definition of an AE will be recorded on the AE page of the eCRFs.

Demographic information and baseline characteristics will be collected at the Screening Visit. Standard demographic parameters include age, sex, and race/ethnicity (recorded in accordance with prevailing regulations). Baseline characteristics will include ECOG PS (Appendix A), disease status, medical histories, prior and concomitant medications, and PE findings.

### 5.3 Agent Administration

Trial treatment should be administered on Day 1 of each cycle after all procedures/assessments have been completed as detailed in the Study Calendar (Section 10). Trial treatment may be administered up to 3 days before or after the scheduled Day 1 of each cycle due to administrative reasons.

All trial treatments will be administered on an outpatient basis.

Pembrolizumab 200 mg will be administered as a 30 minute IV infusion every 3 weeks. Sites

should make every effort to target infusion timing to be as close to 30 minutes as possible.

However, given the variability of infusion pumps from site to site, a window of -5 minutes and +10 minutes is permitted (i.e., infusion time is 30 minutes: -5 min/+10 min).

The Pharmacy Manual contains specific instructions for the preparation of the pembrolizumab infusion fluid and administration of infusion solution.

#### **5.4 General Concomitant Medication and Supportive Care Guidelines**

Medications or vaccinations specifically prohibited in the exclusion criteria are not allowed during the ongoing trial. If there is a clinical indication for one of these or other medications or vaccinations specifically prohibited during the trial, discontinuation from trial therapy or vaccination may be required. The investigator should discuss any questions regarding this with the Merck Clinical team. The final decision on any supportive therapy or vaccination rests with the investigator and/or the subject's primary physician.

- **Diarrhea/Colitis:**  
Subjects should be carefully monitored for signs and symptoms of enterocolitis (such as diarrhea, abdominal pain, blood or mucus in stool, with or without fever) and of bowel perforation (such as peritoneal signs and ileus).
  - All subjects who experience diarrhea/colitis should be advised to drink liberal quantities of clear fluids. If sufficient oral fluid intake is not feasible, fluid and electrolytes should be substituted via IV infusion. For Grade 2 or higher diarrhea, consider GI consultation and endoscopy to confirm or rule out colitis.
  - For **Grade 2 diarrhea/colitis** that persists greater than 3 days, administer oral corticosteroids.
  - For **Grade 3 or 4 diarrhea/colitis** that persists > 1 week, treat with intravenous steroids followed by high dose oral steroids.
  - When symptoms improve to Grade 1 or less, steroid taper should be started and continued over no less than 4 weeks.
- **Nausea/vomiting:** Nausea and vomiting should be treated aggressively, and consideration should be given in subsequent cycles to the administration of prophylactic antiemetic therapy according to standard institutional practice. Subjects should be strongly encouraged to maintain liberal oral fluid intake.
- **Anti-infectives:** Subjects with a documented infectious complication should receive oral or IV antibiotics or other anti-infective agents as considered appropriate by the treating investigator for a given infectious condition, according to standard institutional practice.
- Immune-related adverse events: See Section 6.0 and Events of Clinical Interest Guidance Document for supportive care guidelines, including use of corticosteroids, regarding diagnosis and management of adverse experiences of a potential immunologic etiology.

**Management of Infusion Reactions:** Signs and symptoms usually develop during or

shortly after drug infusion and generally resolve completely within 24 hours of completion of infusion.

Table 3 below shows treatment guidelines for subjects who experience an infusion reaction associated with administration of pembrolizumab (MK-3475).

Table 3 Infusion Reaction Treatment Guidelines

NCI CTCAE Grade	Treatment	Premedication at subsequent dosing

Grade 1            Mild reaction; infusion interruption not indicated; intervention not indicated
	
Increase monitoring of vital signs as medically indicated until the subject is deemed medically stable in the opinion of the investigator.
	
None

Grade 2            Requires infusion interruption but responds promptly to symptomatic treatment (e.g., antihistamines, NSAIDS, narcotics, IV fluids); prophylactic medications indicated for <=24 hrs
	
Stop Infusion and monitor symptoms.            Additional appropriate medical therapy may include but is not limited to:            IV fluids            Antihistamines            NSAIDS            Acetaminophen            Narcotics
 
Increase monitoring of vital signs as medically indicated until the subject is deemed medically stable in the opinion of the investigator.            If symptoms resolve within one hour of stopping drug infusion, the infusion may be restarted at 50% of the original infusion rate (e.g., from 100 mL/hr to 50 mL/hr). Otherwise dosing will be held until symptoms resolve and the subject should be premedicated for the next scheduled dose.
 
Subjects who develop Grade 2 toxicity despite adequate premedication should be permanently discontinued from further trial treatment administration.
	
Subject may be premedicated 1.5h (± 30 minutes) prior to infusion of pembrolizumab (MK-3475) with:
 
Diphenhydramine 50 mg po (or equivalent dose of antihistamine).
 
Acetaminophen 500-1000 mg po (or equivalent dose of antipyretic).

Grades 3 or 4  Grade 3:            Prolonged (i.e., not rapidly responsive to symptomatic medication and/or brief interruption of infusion); recurrence of symptoms
	
Stop Infusion.            Additional appropriate medical therapy may include but is not limited to:            IV fluids            Antihistamines            NSAIDS
	
No subsequent dosing

NCI CTCAE Grade	Treatment	Premedication at subsequent dosing
following initial improvement; hospitalization indicated for other clinical sequelae (e.g., renal impairment, pulmonary infiltrates) Grade 4: Life-threatening; pressor or ventilatory support indicated	Acetaminophen Narcotics Oxygen Pressors Corticosteroids Epinephrine  Increase monitoring of vital signs as medically indicated until the subject is deemed medically stable in the opinion of the investigator. Hospitalization may be indicated. Subject is permanently discontinued from further trial treatment administration.	
Appropriate resuscitation equipment should be available in the room and a physician readily available during the period of drug administration.		

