### 5.5 Supportive Care Guidelines for Immune Related Adverse Events (irAEs)

Adverse events (both non-serious and serious) associated with pembrolizumab exposure may represent an immunologic etiology. These adverse events may occur shortly after the first dose or several months after the last dose of treatment. Pembrolizumab must be withheld for drug-related toxicities and severe or life-threatening AEs as per the Table below. See Section 6.0 for supportive care guidelines, including use of corticosteroids.

Subjects should receive appropriate supportive care measures as deemed necessary by the treating investigator. Suggested supportive care measures for the management of adverse events with potential immunologic etiology are outlined below and in greater detail in the ECI guidance document. Where appropriate, these guidelines include the use of oral or intravenous treatment with corticosteroids as well as additional anti-inflammatory agents if symptoms do not improve with administration of corticosteroids. Note that several courses of steroid tapering may be necessary as symptoms may worsen when the steroid dose is decreased.

If an irAE is suspected, efforts should be made to rule out neoplastic, infectious, metabolic, toxin or other etiologic causes prior to labeling an adverse event as an irAE. Subjects who develop a Grade 2 or higher irAE should be discussed immediately with the overall Principal Investigator or designee. The treatment guidelines are intended to be applied when the investigator determines the events to be related to pembrolizumab.

It may be necessary to perform conditional procedures such as bronchoscopy, endoscopy, or skin photography as part of evaluation of the event. Suggested conditional procedures, as appropriate, can be found in the ECI guidance document.

Note: if after the evaluation the event is determined not to be related, the investigator does not need to follow the treatment guidance (as outlined below). Refer to Section 6.0 for dose modification.

- **Pneumonitis:**
  - For **Grade 2 events**, treat with systemic corticosteroids. When symptoms improve to Grade 1 or less, steroid taper should be started and continued over no less than 4 weeks.
  - For **Grade 3-4 events**, immediately treat with intravenous steroids. Administer additional anti-inflammatory measures, as needed.
  - Add prophylactic antibiotics for opportunistic infections in the case of prolonged steroid administration.
  

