  - For **Grade 2** events, treat with corticosteroids.
  - For **Grade 3-4** events, treat with systemic corticosteroids.
  - When symptoms improve to Grade 1 or less, steroid taper should be started and continued over no less than 4 weeks.
- **Cerebral Edema**

Due to the immunologic nature of pembrolizumab administration, cerebral edema could theoretically result as a consequence of pembrolizumab administration due to immune infiltration of the brain. Symptoms related to cerebral edema may include headache or neurologic deficit that is either new or worsened. Patients with any signs or symptoms of cerebral edema should be treated as clinically appropriate including initiation or increased systemic corticosteroid dosing, treatment with an osmotic diuretic or surgical decompression. Subsequent pembrolizumab dosing should be immediately interrupted if significant clinical symptoms attributable to cerebral edema develop. Treatment with additional pembrolizumab doses may only be re-initiated if clinically significant symptoms attributable to cerebral edema have resolved to grade  $\leq 1$  or pre-treatment baseline. Patients who develop CTCAE 4.0 grade-4 cerebral edema attributable to pembrolizumab administration should not receive further pembrolizumab doses and should discontinue study therapy.

Recommendations to manage irAEs not detailed elsewhere in the protocol are detailed in Table 4.

Table 4 Dose Modification and Toxicity Management Guidelines for Immune-related AEs Associated with Pembrolizumab

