**General instructions:**

1. Corticosteroid taper should be initiated upon AE improving to Grade 1 or less and continue to taper over at least 4 weeks.
2. For situations where pembrolizumab has been withheld, pembrolizumab can be resumed after AE has been reduced to Grade 1 or 0 and corticosteroid has been tapered. Pembrolizumab should be permanently discontinued if AE does not resolve within 12 weeks of last dose or corticosteroids cannot be reduced to  $\leq 10$  mg prednisone or equivalent per day within 12 weeks.
3. For severe and life-threatening irAEs, IV corticosteroid should be initiated first followed by oral steroid. Other immunosuppressive treatment should be initiated if irAEs cannot be controlled by corticosteroids.

Immune-related AEs	Toxicity grade or conditions (CTCAEv 4.0)	Action taken to pembrolizumab	irAE management with corticosteroid and/or other therapies	Monitor and follow-up
Pneumonitis	Grade 2	Withhold	
 
• Administer corticosteroids (initial dose of 1-2 mg/kg prednisone or equivalent) followed by taper
 
	
 
• Monitor participants for signs and symptoms of pneumonitis
 
• Evaluate participants with suspected pneumonitis with radiographic imaging and initiate corticosteroid treatment
 
• Add prophylactic antibiotics for opportunistic infections
 

	Grade 3 or 4, or recurrent Grade 2	Permanently discontinue		
Diarrhea / Colitis	Grade 2 or 3	Withhold	
 
• Administer corticosteroids (initial dose of 1-2 mg/kg prednisone or equivalent) followed by taper
 
	
 
• Monitor participants for signs and symptoms of enterocolitis (ie, diarrhea, abdominal pain, blood or mucus in stool with or without fever) and of bowel perforation (ie, peritoneal signs and ileus).
 
• Participants with <math>\geq</math> Grade 2 diarrhea suspecting colitis should consider GI consultation and performing endoscopy to rule out colitis.
 
• Participants with diarrhea/colitis should be advised to drink liberal quantities of clear fluids. If sufficient oral fluid intake is not feasible, fluid and electrolytes should be substituted via IV infusion.
 

	Grade 4	Permanently discontinue		

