Myocarditis	Grade 1 or 2	Withhold	
 
Based on severity of AE administer corticosteroids
 
	
 
Ensure adequate evaluation to confirm etiology and/or exclude other causes
 

	Grade 3 or 4	Permanently discontinue		
All other immune-related AEs	Intolerable/persistent Grade 2	Withhold	
 
Based on type and severity of AE administer corticosteroids
 
	
 
Ensure adequate evaluation to confirm etiology and/or exclude other causes
 

	Grade 3	Withhold or discontinue based on the type of event. Events that require discontinuation include and not limited to: Guillain-Barre		

		Syndrome, encephalitis		
	Grade 4 or recurrent Grade 3	Permanently discontinue		

1. Withhold or permanently discontinue pembrolizumab is at the discretion of the investigator or treating physician.
 
NOTE:          For participants with Grade 3 or 4 immune-related endocrinopathy where withhold of pembrolizumab is required, pembrolizumab may be resumed when AE resolves to <math>\leq</math> Grade 2 and is controlled with hormonal replacement therapy or achieved metabolic control (in case of T1DM).
				

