### 5.7 Prohibited Concomitant Medication

Subjects are prohibited from receiving the following therapies during the Screening and Treatment Phase (including retreatment for post-complete response relapse) of this trial:

- Antineoplastic systemic chemotherapy or biological therapy
- Immunotherapy not specified in this protocol
- Chemotherapy not specified in this protocol
- Investigational agents other than pembrolizumab
- Radiation therapy
  - Note: Radiation therapy to a symptomatic lesion may be allowed at the investigator’s discretion. If radiation is given to a solitary lesion at the investigator's discretion, then the patient is considered to have progressive disease, but may continue on treatment if patient is clinically stable.
- Live vaccines within 30 days prior to the first dose of trial treatment and while participating in the trial. Examples of live vaccines include, but are not limited to, the following: intranasal influenza vaccines (e.g., Flu-Mist®), measles, mumps, rubella, varicella/zoster, yellow fever, rabies, BCG, and typhoid vaccine.

- Systemic glucocorticoids for any purpose other than to treat edema related to the meningioma or supportive post-operative management or to modulate symptoms from an event of clinical interest of suspected immunologic etiology. Intranasal, inhaled or topical corticosteroids (<5% of body surface area) for the treatment of mild/moderate asthma, allergies or dermatitis are permitted. The use of physiologic doses of corticosteroids may be approved after consultation with the Overall PI. Physiologic replacement of glucocorticoids as maintenance therapy for adrenal insufficiency are permitted. Standard doses of hydrocortisone for maintenance therapy are 10–20 mg/m^2/day divided 2–4 times per day. For a subject with a body surface area (BSA) of 1.73 m^2, this translates to a total dose of 34.6 mg of hydrocortisone per day. The equivalent dose of dexamethasone is 1.2 mg per day. Some subjects may additionally receive mineralocorticoid- replacement maintenance therapy with fludrocortisone. The maintenance dose of fludrocortisone for this indication is 0.05–0.1 mg/day. Antihistamines and other non-steroidal anti-allergy medications are also permitted.

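### Section 5.4 sets a later steroid trigger for Grade 3-4 diarrhea/colitis (more than 1 week) than for Grade 2 (more than 3 days), and no other text in the protocol corrects it

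*Combined protocol and SAP*

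**What the plan says.** Section 5.4 (General Concomitant Medication and Supportive Care Guidelines) has consecutive bullets on diarrhea/colitis. The rule for a Grade 2 event sets this condition and route: "that persists greater than 3 days, administer oral corticosteroids". The next rule, which covers the two more severe grades, sets a longer condition: "that persists > 1 week, treat with intravenous steroids followed by high dose oral steroids". The same list asks sites to watch for enterocolitis and bowel perforation. A later bullet sends events of possible immunologic cause to Section 6.0 and the ECI guidance document, including for steroid use.

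Table 4 in Section 5.5 has its own diarrhea/colitis entry, with this management: "Administer corticosteroids (initial dose of 1-2 mg/kg prednisone or equivalent) followed by taper". Its third general instruction reads: "For severe and life-threatening irAEs, IV corticosteroid should be initiated first followed by oral steroid". Neither gives a waiting period. The sentence introducing the table limits its scope: "Recommendations to manage irAEs not detailed elsewhere in the protocol are detailed in Table 4".

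The diarrhea/colitis row of Table 5 (Section 6) says when to hold, restart and stop pembrolizumab. It does not say when to start steroids.

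**The concern.** A persistence condition on treatment would normally shorten as severity rises. Here it lengthens. On day 5 of an episode, a Grade 2 patient has met the Section 5.4 steroid trigger and a Grade 4 patient has not, although the protocol's own grading table (Table 6) describes Grade 4 as life-threatening and needing urgent intervention. No reason is given for the order.

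What is at stake is patient safety. Section 5.4 names bowel perforation as something to watch for, and a site that followed its trigger to the letter would wait longest in the sickest patients.

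**Working it through.** No statistical figure is involved. The check compares the printed rules.

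**1. The two triggers in Section 5.4**

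| Grade | Steroid trigger | Route |
|---|---|---|
| 2 | more than 3 days | oral |
| 3 or 4 | more than 1 week (7 days) | IV, then high-dose oral |

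Difference: 7 − 3 = 4 days, in the wrong direction.

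**2. Table 4 rows that include Grade 3 or 4**

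There are 12: pneumonitis 3-4; diarrhea/colitis 2-3; diarrhea/colitis 4; AST/ALT/bilirubin 3-4; type 1 diabetes or Grade 3-4 hyperglycemia; hypophysitis 3-4; hyperthyroidism 3-4; hypothyroidism 2-4; nephritis 3-4; myocarditis 3-4; other Grade 3; other Grade 4 or recurrent Grade 3.

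Three of these prescribe no corticosteroid in the management column: diabetes/hyperglycemia (insulin or anti-hyperglycemic), hyperthyroidism (beta-blockers or thionamides) and hypothyroidism (thyroid hormone). They say nothing about steroid timing, so they drop out: 12 − 3 = 9.

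Rows among the 9 with a persistence condition: 0. In 7 of the 9 the management cell is blank in the extracted text and is read as merged with the cell above; the 2 with their own printed cell are diarrhea/colitis 2-3 and AST/ALT/bilirubin 3-4. The only persistence wording in Table 4's grade column is "Intolerable/persistent Grade 2", for all other immune-related events, and it has no day count.

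**3. Section 5.5 prose**

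Five Grade 3-4 bullets call for steroids: pneumonitis, hypophysitis, hyperthyroidism, hepatic, renal. Bullets with a wait: 0. The pneumonitis bullet says to treat at once. The 24 to 48 hours in the hepatic bullet is a duration of treatment. The prose has no diarrhea/colitis bullet, so Section 5.4 is the only prose steroid instruction for that event.

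**4. Which text governs**

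- The irAE bullet in Section 5.4 points to Section 6.0, which has no steroid start trigger, and to the ECI guidance document. Only the title of that document (Appendix B) is in the text available for this review, so its content cannot be judged.
- That bullet does not point to Table 4.
- Table 4 is introduced as covering irAEs not detailed elsewhere. Diarrhea/colitis is detailed in Section 5.4, so a literal reader could conclude that the one-week rule stands.

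**5. Whether Section 5.4 covers only ordinary diarrhea**

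This is hard to sustain. The bullets name colitis, and their taper (start at Grade 1 or less, over at least 4 weeks) matches the one used for irAEs in Section 5.5. Section 5.7 restricts systemic glucocorticoids to meningioma-related edema, post-operative care, physiologic dosing or replacement, and use to "modulate symptoms from an event of clinical interest of suspected immunologic etiology". High-dose steroids for plain diarrhea would fit none of these.

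**The case against.** The strongest reply is that the two texts apply at different stages. Section 5.5 asks sites to rule out infectious and other causes before labelling an irAE, and applies its guidance once the investigator judges the event related to pembrolizumab. Section 5.4 could then cover diarrhea before attribution and Table 4 the attributed event. Section 5.7 is compatible with this, since a suspected immune cause is enough to permit steroids. This reading removes much of the tension between sections. It does not explain why, inside Section 5.4, Grade 3-4 should wait longer than Grade 2.

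A reader might infer that Table 4 requires steroids at onset and so directly contradicts any wait. The documents do not support that. Table 4 is silent on timing, and its third general instruction sets a sequence (IV, then oral) that Section 5.4 also follows. The mismatch is between a stated delay and an instruction with no condition attached.

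A reader might also infer that Section 5.4 forbids earlier steroids. It does not. The section is headed as guidelines and leaves the final decision on supportive therapy to the investigator and/or the patient's primary physician. GI consultation and endoscopy are to be considered from Grade 2. Section 5.5 adds: "Subjects who develop a Grade 2 or higher irAE should be discussed immediately with the overall Principal Investigator or designee". Pembrolizumab is withheld at Grade 2-3 and stopped at Grade 4. These safeguards stand and reduce the practical risk, but they work around the written trigger without correcting it. Holding drug is not an instruction on steroids.

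Finally, the ECI guidance document may give the right timing. That is possible, and it is why the final wording should be checked against it.

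**Conclusion.** The Section 5.4 trigger is wrong as written and should be fixed. The steroid trigger for Grade 3-4 diarrhea/colitis comes 4 days later than for Grade 2, and it is the only wait attached to a Grade 3-4 steroid instruction when set against the 9 relevant Table 4 rows and the 5 Section 5.5 bullets. The order within Section 5.4 can be read directly from the page. Which text governs is less certain, because one of the two cross-references leads to a document whose content is not available here. The row count assumes that the blank management cells in Table 4 are merged cells.

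The counts describe printed rules. They do not estimate harm, and the documents give no basis for such an estimate. PFS6, the sample size and the decision rule (at least 10 of 24 patients) are unaffected.

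**What to change.** 1. Reword the Grade 3-4 bullet in Section 5.4 so that Grade 3 or 4 diarrhea/colitis of suspected immune-related cause is treated with IV and then high-dose oral steroids, with no persistence condition. The immune-cause qualifier must be in the bullet itself. Striking the one-week phrase alone would direct IV steroids at any Grade 3-4 diarrhea, including infectious diarrhea, which would sit badly with the work-up asked for in Section 5.5 and the steroid limits in Section 5.7.
2. Add one sentence stating that Table 4 governs immune-related diarrhea/colitis.
3. Have the sponsor's safety physicians check the wording against the ECI guidance document. This should include the Grade 2 three-day interval, which also has no counterpart in Table 4.

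The cost is a wording amendment: one bullet reworded and one sentence added, with no extra procedures, patients or staff.
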